7 DATA QUALITY ASSURANCE

An independent angiographic committee of experts may be consulted to blindly analyze cases to check for validity of exclusion and inclusion criteria and other relevant aspects of the study.

Document ID:	<As applicable, per local requirements>	Document title:		Classification:	For internal use
		Statistical Analysis Plan			
Modified:	11MAY2023	Template ID:	ClinicalStudyTemplate0025	Author:	
Version:	3.0	Template Version Date:	02MAR2018	Approver:	
Status:	Final			Page:	20 of 52

Statistical Analysis Plan

8 STATISTICAL METHODS

8.1 Sample Size

We plan to include 394 subjects in the study, the maximum number of subjects needed for the analysis of the primary and secondary endpoint. We target to limit the enrollment duration of the 394 subjects to a 9 months maximum, which translates to minimally 10 subject inclusions per week overall. Based on a typical PCI procedure volume and the inclusion and exclusion criteria it is feasible to enroll at least 2 subjects per week per center, i.e., at least 5 centers are required.

8.1.1 Sample Size Justification Primary Endpoint

A recent single center, non-randomized, retrospective study [Yabe 2018] has shown to achieve 21.9% contrast reduction when using Dynamic Coronary Roadmap compared to the control group without using Dynamic Coronary Roadmap, see Table 2.

	Control group	DCR group
Number of patients	103	43
Iodinated contrast volume (ml) average \pm standard deviation	152.1 ± 73.0	118.8 ± 49.7

Table 2 Results of a recent pilot study [Yabe 2018]

To determine the sample size for the primary endpoint of this study we used the Yabe study outcomes as input with a margin of 7% for the contrast reduction, i.e., the sample size calculation is performed to reliably show a 15% contrast reduction in the DCR group compared to the control group not using Dynamic Coronary Roadmap.

For the sample size and power calculations we have set:

- Estimated mean for the Control group = 152.1 (based on [Yabe 2018])
- Estimated mean for the DCR group = 129.3 (15% reduction)
- Estimated standard deviation = 73.0 (based on [Yabe 2018])
- Effect size (standardized difference): $(152.1 - 129.3)/73.0 = 0.3123$
- Significance: one-sided $\alpha = 0.025$ (the type I error, i.e., probability of rejecting a true null hypothesis)

Document ID:	<As applicable, per local requirements>	Document title:		Classification:	For internal use
		Statistical Analysis Plan			
Modified:	11MAY2023			Author:	
Version:	3.0	Template ID:	ClinicalStudyTemplate0025	Approver:	
Status:	Final	Template Version Date:	02MAR2018	Page:	21 of 52

Statistical Analysis Plan

- Power (1- β) = 80%

Sample sizes of 162 for each group achieves 80% power to reject the null hypothesis of equal means when the population mean difference is 15% with a standard deviation of 73.0 for both groups and with a significance level (alpha) of 0.025 using a one-sided two-sample equal-variance t-test (calculated by PASS 16.0.3 software).

Finally the percentage of subjects that are expected to be lost at random during the course of the study (drop-out rate) and for whom no response data will be collected (i.e., will be treated as "missing") needs to be taken into account. A drop-out rate of 10% (DR=0.1) is assumed, meaning that $162/(1-DR)=180$ patients are needed in each group totaling 360 patients for the primary endpoint.

The study will be a multi-center trial in which per center a maximum of three investigators will be participating and each investigator is required to include at least 20 patients in the study, which indirectly sets the minimum number of subjects to be included per center.

8.1.2 Sample Size Justification Secondary Endpoint

A recent single center, non-randomized, prospective study [Rajappan 2017] showed a 25.6% reduction in the median number of cine X-ray runs after introduction of Dynamic Coronary Roadmap, see Table 3.

	Enrollment group 1	Enrollment group 4
Number of patients	21	21
Number of cine X-ray runs	Average: 46.2 SD: 22.4 Median: 43.0 IQR: 31-54	Average: 34.6 SD: 21.2 Median: 32.0 IQR: 20-43
Number of stents	Average: 1.76 SD: 0.89	Average: 1.67 SD: 0.86

Table 3 Results of a recent pilot study [Rajappan 2017]

For the sample size and power calculations we have set based on [Rajappan 2017]:

- Estimated mean for the Control group = 46.2
- Estimated mean for the DCR group = 34.6

Document ID:	<As applicable, per local requirements>	Document title:	Classification:	For internal use
Modified:	11MAY2023	Statistical Analysis Plan		
Version:	3.0	Template ID:	ClinicalStudyTemplate0025	Approver:
Status:	Final	Template Version Date:	02MAR2018	Page: 22 of 52

Statistical Analysis Plan

- Estimated median for the Control group = 43.0
- Estimated median for the DCR group = 32.0
- Significance: one-sided $\alpha = 0.025$ (the type I error, i.e., probability of rejecting a true null hypothesis)
- Power $(1-\beta) = 80\%$

Sample sizes of 177 for each group achieves 80% power to reject the null hypothesis of equal population distributions with a significance level (alpha) of 0.025 using a one-sided Wilcoxon-Mann-Whitney test, since the number of angiographic X-ray runs is discrete and is likely to be not normally distributed (calculated by SAS software).

This means for the secondary endpoint on Number of Angiograms that $177/(1-DR)=197$ patients are needed in each group, so 394 in total which is higher than the total number of patients (360) required for the primary endpoint, so **a total of 394 subjects are required for this study.**

8.2 General Considerations

All results will be summarized by treatment group using the following descriptive statistics: n, mean with 95% confidence intervals, standard deviation (SD), median, interquartile range (IQR), minimum and maximum. Categorical data will be summarised for each treatment group as the number and percentage of subjects in each category (including the category 'missing' if applicable). Generally, percentages will be calculated for missing categories and all percentages will be based on total number of subjects in the population (denoted by N on the summary tables and figures) Statistical analysis will be performed using SAS (SAS® Life Science Analytics Framework 5.1.2) and/or R statistical software (<https://www.r-project.org/>).

All data will be listed for the enrolled population. The data will be sorted by treatment group, subject number and date of assessment (if applicable).

All hypotheses will be tested at a 2.5% level of significance using a one-sided test unless otherwise specified.

For summary statistics, the mean and median will be displayed to one decimal place greater than the original value and the measure of variability (e.g., SD) will be displayed to two decimal places greater than the original value. Minimum and maximum will be reported to the same decimal places as the original value. Percentages will be displayed to 1 decimal place. P-values will be reported to three decimal places; p-values less than 0.001 will be reported as $p<0.001$.

Summary tables will have treatment columns labelled as 'Dynamic Coronary Roadmap' or 'Control'. The main data will also be presented per clinical site.

Document ID:	<As applicable, per local requirements>	Document title:		Classification:	For internal use
		Statistical Analysis Plan			
Modified:	11MAY2023			Author:	
Version:	3.0	Template ID:	ClinicalStudyTemplate0025	Approver:	
Status:	Final	Template Version Date:	02MAR2018	Page:	23 of 52

Statistical Analysis Plan

8.2.1 Analysis Population

The following analysis populations will be defined in this study.

Enrolled Population

The enrolled population is defined as all subjects who signed informed consent.

Randomized population

The randomised population is defined as all randomised subjects, defined as any subject with a randomisation result as recorded in the eCRF.

Analysis of data using the randomised population will consider allocation of subjects to treatment groups as randomised.

Full Analysis Population

The full analysis population (FAP) is defined as all randomised subjects who underwent a PCI in at least one vessel without the use of OCT and/or rotational or orbital atherectomy of which the primary endpoint and/or the secondary endpoint is available.

Analysis of data using the Full analysis population will consider allocation of subjects to treatment groups as randomised.

Safety population

The safety analysis population (SAF) is defined as all randomised subjects who underwent a(n) attempt to PCI or another procedure (for example CABG).

Analysis of data using the Safety population will consider allocation of subjects to treatment groups as treated (i.e. will be based on the actual treatment a subject has received regardless of which treatment they were randomised to receive).

In case the safety population is equal to the full analysis population, only the results of the full analysis population will be presented.

Per Protocol population

The Per Protocol population is defined as all FAP subjects without major protocol violations. Protocol violations are failures to adhere to the inclusion/exclusion criteria and protocol requirements and will be divided into major protocol violations and minor protocol violations. Major protocol violations are those that are considered to have a significant effect on the treatment efficacy and hence would exclude the subject from the PP population. Minor protocol violations are those that are not considered to significantly affect the efficacy evaluation and

Document ID:	<As applicable, per local requirements>	Document title:	Classification:	For internal use
Modified:	11MAY2023	Statistical Analysis Plan		
Version:	3.0	Template ID:	ClinicalStudyTemplate0025	Approver:
Status:	Final	Template Version Date:	02MAR2018	Page: 24 of 52

Statistical Analysis Plan

hence do not warrant subjects' exclusion from the PP population. Major protocol violations will be identified by a Data Review Meeting prior to database lock.

The following criteria might be considered as major protocol violations:

- (1) Violation of any inclusion or exclusion criteria
- (2) Errors in treatment assignment (i.e. actual treatment differs from the randomised treatment)

Analysis of data using the Per Protocol population will consider allocation of subjects to treatment groups as randomised.

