6.4.5. Procedure for the replacement of subjects

In enrolled subjects the investigator preprocedurally deemed no usage of OCT and/or the rotational or orbital atherectomy is required. During the PCI procedure usage of OCT and/or rotational or orbital atherectomy is left to the investigator's discretion. In the case OCT and/or rotational or orbital atherectomy is used in enrolled subjects, these subjects will be replaced.

Thus, the following subjects will be replaced:

- Subjects undergoing PCI supported by OCT will be replaced.
- Subjects undergoing PCI supported by rotational or orbital atherectomy will be replaced.

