4.4.2 Randomization

The randomization will be performed via the Electronic Data Capture (EDC) system hosting the electronic Case Report Form.

In order to ensure balance of the treatment groups across subgroups, we stratified the randomization by site and within site by type of PCI (ad hoc or elective) and the number of vessels to be treated via PCI, i.e., 1, 2, or 3 or more vessel PCI. Within the subgroups we will perform a permuted block design. We will use a block size of 4 patients per block. There will be an equal allocation to the PCI procedure with DCR and the PCI procedure without the use of DCR (1:1 randomization).

In case of elective PCI, randomization will be done before the procedure and in case of ad hoc PCI randomization will be done upon decision to go for PCI right after diagnostics, so when the patient on the table still.

In enrolled subjects the investigator pre procedurally deemed no usage of OCT and/or the rotational or orbital atherectomy is required. During the PCI procedure usage of OCT and/or rotational or orbital atherectomy is left to the investigator's discretion.

In the case OCT and/or rotational or orbital atherectomy is used in enrolled subjects, these subjects will be replaced. When the decision is made to replace a subject this subject will not count for the required total number of subjects total, but will still be part of the Safety population. A new subject will be randomized to either of the arms.

Document ID:	<As applicable, per local requirements>	Document title:		Classification:	For internal use
		Statistical Analysis Plan			
Modified:	11MAY2023	Template ID:	ClinicalStudyTemplate0025	Author:	
Version:	3.0	Template Version Date:	02MAR2018	Approver:	
Status:	Final			Page:	11 of 52

Statistical Analysis Plan

Thus, the following subjects will be replaced:

- Subjects undergoing PCI supported by OCT will be replaced.
- Subjects undergoing PCI supported by rotational or orbital atherectomy will be replaced.

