4.5 Control to Minimize Bias

Ideally the study should be blinded, because there is potential intrinsic bias (sometimes referred to as the Hawthorne Effect) due to the fact the participants know that they are participating in a clinical study and know which arm they are participating in. However, as the Dynamic Coronary Roadmap is a visualization tool the study cannot be blinded.

Only standard guiding catheters will be used in the study and devices that could potentially confound contrast usage (e.g. rotational or orbital atherectomy device) will be excluded.

The methods to check whether the PCI was successful can include angiography, Stent Boost, and/or IntraVascular UltraSound (IVUS). Some of these procedures can include contrast agent volume, whereas others specifically do not (e.g., Stent Boost is a software feature). Therefore, the choice for checking the PCI result could introduce a bias based on individual users' preferences. Some PCI check methods are potential confounders for contrast usage and we will investigate to take measures to reduce the risk of bias based on site differences and user preferences. During site initiation it has been communicated that the PCI check procedure is to be standardized in both arms, which is standard of practice. This will be checked via remote monitoring of the eCRFs.

Analyses to determine whether there is an effect based on e.g. intervention difficulty (measured by the SYNTAX score), lesion characteristics, patient demographics, physician experience, center effect etc. will be performed. If an effect is found applying adjustment analysis, i.e. analysis of covariance adjusting for relevant confounders will be considered as a sensitivity analysis.

Document ID:	<As applicable, per local requirements>	Document title:	Classification:	For internal use
Modified:	11MAY2023	Statistical Analysis Plan		
Version:	3.0	Template ID:	ClinicalStudyTemplate0025	Approver:
Status:	Final	Template Version Date:	02MAR2018	Page: 12 of 52

Statistical Analysis Plan

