8.11 Efficacy Analysis

All efficacy outcomes will be presented for the Full Analysis Population and the Per Protocol Population.

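### The full analysis population drops randomised patients when an unblinded operator chooses OCT or atherectomy, and no planned analysis clearly gives an as-randomised estimate that includes them

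*SAP*

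**What the plan says.** SAP section 4.4.2 states: "During the PCI procedure usage of OCT and/or rotational or orbital atherectomy is left to the investigator's discretion". Protocol section 6.4.5 gives the consequence: "In the case OCT and/or rotational or orbital atherectomy is used in enrolled subjects, these subjects will be replaced". The SAP adds, "When the decision is made to replace a subject this subject will not count for the required total number of subjects total"; these subjects stay in the Safety population. Section 4.5 concedes that "as the Dynamic Coronary Roadmap is a visualization tool the study cannot be blinded" and gives the reason for the restriction: "devices that could potentially confound contrast usage (e.g. rotational or orbital atherectomy device) will be excluded".

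Section 8.2.1 then defines the FAP as "all randomised subjects who underwent a PCI in at least one vessel without the use of OCT and/or rotational or orbital atherectomy", provided the primary or secondary endpoint is available. Section 8.11 says: "All efficacy outcomes will be presented for the Full Analysis Population and the Per Protocol Population". Sections 8.11.1 and 8.11.2 place the primary and secondary tests in the FAP and repeat them in the per-protocol set. The protocol (7.6 and 7.7.1) had said that all subjects would be analysed; SAP section 9.2 narrows this to the FAP.

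**The concern.** Membership of the primary analysis set depends on a decision made after allocation, by someone who knows the allocation, about techniques that the SAP itself links to contrast use. If the roadmap changes how often an operator turns to OCT or atherectomy, or in which patients, the retained groups are no longer the groups that were randomised. Part of the observed difference in contrast volume could then come from who was removed. The secondary endpoint, number of angiograms, is exposed in the same way.

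A supportive analysis that keeps these patients in their randomised arms would show whether this matters. The plan does not clearly contain one, so a reader of the final report could not tell whether the result depends on the exclusion.

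**Working it through.** **Which analyses could include these patients**

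- FAP: excludes them by definition.
- Per-protocol set: FAP subjects without major violations, so it excludes them too.
- Worst-case imputation (8.2.2, 8.11.1): run in the FAP.
- Covariate and centre models (8.14): no population named, but 8.11 limits efficacy to FAP and per-protocol.
- Randomised population: grouped as randomised, but the table list in section 11 uses it only for site counts, stratification factors, disposition, population counts and demographics.
- Safety population: includes them, and section 8.10 summarises total contrast read-out and number of angiograms by group. It is grouped as treated, also holds attempted PCI and other procedures such as CABG, and has no planned between-arm estimate or test for either endpoint.

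**The plan's own figure**

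Inputs from SAP 8.1.1: means 152.1 and 129.3 ml (difference 22.8 ml), SD 73.0 ml, one-sided alpha 0.025, power 80%. The noncentral t calculation gives 162 per arm (power 80.03%). With 10% drop-out, 162/0.9 = 180 per arm, 360 in total. This reproduces. At 177 per arm, the number evaluable for the secondary endpoint, power for 22.8 ml is 83.4%.

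**Size of the shift**

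Let pC and pD be the excluded shares in the control and DCR arms, and E the mean excess contrast volume of excluded over retained patients, taken as equal in both arms. Retained mean = arm mean − pE, so

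FAP difference (control − DCR) = as-randomised difference + (pD − pC) × E.

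With 177 retained per arm, SE = 73 × √(2/177) = 7.76 ml. If the as-randomised means are equal, one-sided alpha = 1 − Φ(1.96 − shift/SE). The documents give no values for pC, pD or E; all are assumptions here, with E in units of the 73 ml SD.

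| Control / DCR excluded | E | Shift (ml) | % of 22.8 ml | Alpha |
|---|---|---|---|---|
| equal rates | any | 0 | 0 | 2.5% |
| 1% / 2% | 1 SD | 0.73 | 3% | 3.1% |
| 2% / 4% | 1 SD | 1.46 | 6% | 3.8% |
| 5% / 10% | 0.5 SD | 1.83 | 8% | 4.2% |
| 5% / 10% | 1 SD | 3.65 | 16% | 6.8% |
| 5% / 10% | 1.5 SD | 5.48 | 24% | 10.5% |
| 10% / 5% | 1 SD | −3.65 | −16% | 0.75% |

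Of 197 per arm, 1% against 2% is about 2 against 4 patients, and 5% against 10% about 10 against 20. In the last row the bias works against DCR: power at the design effect falls from 83.4% to 69.2%, because the expected FAP difference is 22.8 − 3.65 = 19.15 ml.

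A simulation of 40,000 trials (191 randomised per arm, 5%/10%, E = 1 SD, equal as-randomised means) gave alpha of 6.9% in the FAP and 2.6% as randomised. The two estimates differed by 3.64 ml on average.

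**The case against.** The restriction was declared in advance with a stated reason, and some safeguards exist. The investigator must judge both techniques unnecessary before the procedure, diagnostic angiography precedes allocation, and randomisation is stratified by site, PCI type and number of vessels. These points suggest few cases. They all act before allocation, though, and the exclusion comes after it.

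The strongest statistical objection is that the alphas depend on the null chosen. If the means are equal among retained patients rather than in the whole arms, the same simulation gives about 2.6% for the FAP and 0.8% as randomised. That stands: the figures do not prove the FAP test wrong. They show how far the two answers can part, which is the reason to report both. It also stands that no rate or excess is documented, that the low scenario is small, and that the figures are on the raw scale while SAP Tables 29/30 list a log-transformed primary analysis. If volumes are lognormal with the design mean and SD, the 6.8% becomes about 6.0%.

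The SAP also plans disposition tables and a listing of reasons for non-evaluation, plus listings of randomisation, contrast use and number of runs. A reader might rebuild an as-randomised comparison from the listings. None of this is a planned effect estimate.

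Finally, the supportive set proposed here itself requires PCI started and an endpoint recorded. It is closer to as-randomised than the FAP, not free of selection, so those losses need reporting by arm too.

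**Conclusion.** The concern holds and should be fixed. The FAP excludes on a post-randomisation decision by an unblinded operator, and every inferential efficacy analysis with a named population sits in the FAP or a subset of it. This rests on the text and is firm.

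The bias is possible, not demonstrated. Under the assumed rates and excesses it runs from zero to about 5.5 ml of the planned 22.8 ml, in either direction depending on which arm loses more patients.

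A smaller, separate point: the phrase about at least one vessel in the FAP definition can be read as keeping a multivessel patient in whom OCT or atherectomy was used in only one vessel. The replacement rule covers any subject in whom either was used. FAP membership of such patients is open to interpretation.

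**What to change.** Keep the FAP as the primary set and make three changes to the SAP.

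1. In 8.2.1, 8.11.1 and 8.11.2, add a mandatory supportive analysis, grouped as randomised, of all randomised subjects in whom PCI was started and the endpoint was recorded in the primary window (first stable guiding-catheter position to end of PCI). Include OCT and atherectomy cases and replaced subjects. Beside the FAP result, report the estimate, 95% confidence interval and p-value for contrast volume, with the same test and transformation, and the same Wilcoxon test for angiograms.
2. Report by randomised arm the number removed for OCT or atherectomy, with their primary-window contrast volume, and separately the number removed for no PCI or no endpoint.
3. Reconcile the FAP wording with the replacement rule so that the status of multivessel patients is fixed. The supportive set contains them under either reading.

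The cost is SAP wording and one extra table set. Protocol section 6.5 records contrast at both time points with no exception for these cases, so the data should exist. The FAP test, its power and the replacement rule are unchanged.

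Precision is similar because replaced subjects come on top of the required total. The 95% half-width is 15.3 ml in the FAP (177 per arm). In the supportive set, with n = 177/(1 − p) rounded down and SD = 73 × √(1 + p(1 − p)), it is 15.3 ml at p = 1% (178 per arm) and 15.1 ml at p = 10% (196 per arm), for a 73 ml excess. The downside is a second estimate that may differ from the first and would have to be explained.

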7.8.10. Sensitivity Analysis for the Primary Endpoint

A worst-case analysis will be considered for the primary endpoint [the average total undiluted iodinated contrast volume (in ml) used per PCI]. For missing outcomes for the control group, the lower bound of the 95% confidence interval around the control mean will be imputed. For missing outcomes for the DCR group, the upper bound of the 95% confidence interval around the DCR mean will be imputed. The primary endpoint will be re-assessed with a complete dataset.

8. Data management

An e-CRF will be used to collect medical history, subjects demographics, procedure related information, protocol deviations, adverse events and device deficiencies.

The e-CRF will be used for data review, data cleaning and issuing and resolving queries. This e-CRF is a web-based e-CRF which is password protected and is 21 CFR part 11 compliant. At the end of the study the data will be stored as a frozen dataset and will be retained. Interview can be performed separately from the e-CRF.

The e-CRF data from the subjects will be key-coded (pseudonymized). The information related to the subjects (like name) is kept separately in the enrollment log at the hospital. Date and time of the procedure and date of discharge will be collected.

All exported (image) data will be de-identified and this data will be collected and stored in a secure location.

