The results of the t-test will be displayed as estimates of the between treatment group difference (with 95% confidence intervals) and the (one-sided) p-value for the between treatment group difference. When the p-value is lower than the significance level of 2.5% (alpha) we will reject the null hypothesis.

The primary analysis will be repeated for the PP population.

In addition and for sensitivity purposes a worst-case analysis will be considered for the primary endpoint. For missing outcomes for the control group, the lower bound of the 95% confidence interval around the control mean will be imputed. For missing outcomes for the DCR group, the upper bound of the 95% confidence interval around the DCR mean will be imputed. The primary endpoint will be re-assessed with a complete dataset for the FAP population.

As a descriptive analysis, the (V) to creatinine clearance GFR ratio will be calculated. Assuming a contrast volume reduction by DCR, the contrast volume/GFR ratio will give information on how clinically meaningful this contrast reduction is. The ratio will be calculated by dividing the volume of contrast volume (in ml) received by the patients' GFR (in ml/min/1.73m²).

Document ID:	<As applicable, per local requirements>	Document title:		Classification:	For internal use
Modified:	11MAY2023	Statistical Analysis Plan		Author:	
Version:	3.0	Template ID:	ClinicalStudyTemplate0025	Approver:	
Status:	Final	Template Version Date:	02MAR2018	Page:	29 of 52

Statistical Analysis Plan

The CKD-EPI equation to estimate the glomerular filtration rate reads [Levey 2009]:

$$eGFR = 141 * \min(SCr/K, 1)^\alpha * \max(SCr/K, 1)^{-1.209} * 0.993^{Age} * 1.018 \text{ [if female]} * 1.159 \text{ [if black]}$$

with $K=0.7$ and $\alpha=-0.329$ if female

with $K=0.9$ and $\alpha=-0.411$ if male

Here min indicates the minimum of SCr/K or 1, and max indicates the maximum of SCr/K or 1. In case the race is unknown we will use 1 as multiplication factor.

As recommended by the ESC/EACTS Guidelines, the total contrast volume/GFR ratio should not exceed 3.7, because when the ratio is larger than 3.7 the risk for severe CKD ($eGFR < 30$) increases significantly [Laskey 2007, Neumann 2018].

The average V/GFR ratio (with 95% CI) and the proportion of patients with a V/GFR ratio > 3.7 (with 95% exact CI) will be presented by treatment group for the FAP.

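### The worst-case missing-data analysis is confined to the Full Analysis Population, so randomised subjects with neither endpoint can never be imputed

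*SAP*

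**What the plan says.** SAP 8.1.1 allows for 10% drop-out and describes these subjects as people "for whom no response data will be collected", to be handled as missing. SAP 8.1.2 applies the same rate to the secondary endpoint, which sets the total of 394.

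SAP 8.2.1 defines the FAP by three conditions: randomised; PCI in at least one vessel without OCT or atherectomy; and endpoint data, in the words "of which the primary endpoint and/or the secondary endpoint is available". SAP 8.11 presents efficacy outcomes for the FAP and the Per Protocol population only, and the latter is a subset of the FAP.

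For missing contrast volumes, SAP 8.11.1 imputes the lower 95% confidence limit of the control mean in the control arm and the upper limit of the DCR mean in the DCR arm. It then says: "The primary endpoint will be re-assessed with a complete dataset for the FAP population". SAP 8.2.2 gives the same imputation rule without naming a population.

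Protocol 7.8.10 describes the analysis with no such restriction: "The primary endpoint will be re-assessed with a complete dataset". Both documents say only that the analysis is to be considered. SAP 9.2 declares that the protocol's inclusion of all subjects has become the FAP, but does not discuss what this does to the missing-data analysis.

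**The concern.** A worst-case analysis is there to show how far the result depends on subjects whose outcome was not observed. Here the population definition screens out the subjects with no outcome data before the imputation rule can reach them. The analysis would then look stable whatever the number or pattern of such losses.

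Loss after allocation is possible. The trial is unblinded, consent may be withdrawn at any time, and elective subjects are randomised before the procedure starts. If losses differed between arms, this planned check could not show their effect on the estimate. A reader of the final report could also take a complete-dataset analysis to cover every randomised subject with a missing volume, which it would not.

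**Working it through.** **Who can be imputed.** Take a randomised subject who had a qualifying PCI and compare data status with the FAP rule:

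| Contrast volume | Angiogram count | In FAP? | Imputed under SAP 8.11.1? |
|---|---|---|---|
| observed | observed or missing | yes | not needed |
| missing | observed | yes | yes |
| missing | missing | no | no |

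The last row is the drop-out of SAP 8.1.1. A randomised subject who had no PCI is also outside the FAP.

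**Inputs (SAP 8.1.1 and 8.1.2).** Control mean 152.1 ml; DCR mean 129.3 ml; difference 22.8 ml; SD 73.0 ml in both arms; one-sided alpha 0.025; drop-out 10%; 177 evaluable per arm.

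**The plan's own figures.** The exact noncentral-t calculation gives power 0.7978 at 161 per arm and 0.8003 at 162, so 162 is reproduced. 162/0.9 = 180 per arm, 360 in total. 177/0.9 = 196.7, rounded up to 197 per arm, 394 in total.

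**How many could be left out.** 197 − 177 = 20 per arm, about 40 in total (394 × 10% = 39.4). This is an upper figure within the planned allowance: it assumes that every planned drop-out lacks both endpoints.

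**Effect of including 20 per arm under the SAP's rule.**

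- Half-width of the 95% interval: t(0.975; 176) × 73/√177 = 10.83 ml.
- Imputed values: control 152.1 − 10.83 = 141.3 ml; DCR 129.3 + 10.83 = 140.1 ml.
- Each arm mean moves by (20/197) × 10.83 = 1.10 ml: control 151.0, DCR 130.4.
- Difference: 22.8 − 2 × 1.10 = 20.6 ml.
- SD: √{[176 × 73² + 177 × 1.10² + 20 × (10.83 − 1.10)²]/196} = 69.3 ml.
- Before imputation: SE = 73 × √(2/177) = 7.76; t = 22.8/7.76 = 2.94; one-sided p = 0.0018.
- After imputation: SE = 69.3 × √(2/197) = 6.98; t = 20.6/6.98 = 2.95; one-sided p = 0.0017.

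The estimate falls, but constant imputed values shrink the SD, so the test statistic does not fall.

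**Borderline case.** With 177 per arm, p = 0.025 corresponds to an observed difference of 15.26 ml. Imputing 20 per arm by the same rule gives 15.26 − 2.20 = 13.06 ml, t = 1.87 and p = 0.031.

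These figures use the untransformed ml scale and equal variances. SAP 8.11.1 allows a log transformation, for which the documents give no planning values.

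**The case against.** Five points can be made for the plan.

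- **The analysis is not empty.** The two endpoints come from different sources, the injector and a visual count of runs. A lost injector reading with countable runs keeps the subject in the FAP, and that subject is imputed. This stands. A reader might infer that none of the 40 planned drop-outs would be imputed, but the documents do not support that: the 10% is a planning allowance applied to each endpoint in turn, and no split between losing one endpoint and losing both is given.

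- **The effect on the test is negligible at the planning values.** This also stands. The imputed values are mild, and changing the population alone does not make the check demanding. What value to impute is a separate question. No rule, however strict, can test the effect of subjects who are not in the dataset.

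- **Drop-outs are already visible.** SAP 8.3 plans a listing of reasons for non-evaluation, and the SAP's table list includes disposition, non-completion reasons and analysis populations by randomised arm. These count the losses by arm but do not show what the losses could do to the estimate.

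- **SAP 8.2.2 names no population and mentions multiple imputation.** But 8.11.1 names the FAP for this analysis, and multiple imputation is only an example of what might be done if missingness is judged non-ignorable. At best the two sections leave an ambiguity.

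- **Not every randomised subject can sensibly be imputed.** A volume used per PCI does not exist for someone who had no PCI, and the Randomized population also contains replaced OCT and atherectomy subjects who may have observed volumes. This is right, and it limits the fix.

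**Conclusion.** The point holds as a defect in the population chosen for the sensitivity analysis. As written, randomised subjects with neither endpoint cannot be imputed, although they are the kind of drop-out that the sample size allows for. The number affected is at most about 20 per arm under the planned 10%, and the true number is unknown.

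Under the SAP's own rule and planning values, the omission is worth about 2.2 ml on the estimate (22.8 against 20.6 ml). One-sided p is about 0.002 either way; a borderline 0.025 would become about 0.031. These figures assume 20 losses in each arm, all without either endpoint, and a common SD of 73 ml.

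Two stronger readings are not supported. The first is that the primary conclusion is shown to be unsafe: at the planning values it does not change. The second is that the SAP withdraws a firm protocol commitment: Protocol 7.8.10 also says only that the analysis will be considered, and SAP 9.2 openly declares the move from all subjects to the FAP.

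**What to change.** In SAP 8.2.2 and 8.11.1:

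- Replace the statement that the analysis will be considered with a commitment to run it on the Randomized population, by randomised arm.
- Impute every subject who had a PCI, or whose PCI status is unknown, and who has no contrast volume, including those with neither endpoint.
- For replaced OCT and atherectomy subjects, either use their observed volumes or exclude them by a stated rule, with counts per arm.
- Report randomised subjects who had no PCI separately, by arm and reason, and do not impute a per-PCI volume for them.
- State the number imputed in each arm and the reason for each missing value.
- Keep the FAP for the primary test.

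The cost is some SAP wording and one extra run on a population the SAP already defines. The sensitivity estimate is likely to be slightly less favourable to DCR.
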